3.0 Objectives/Aims

Aim 1: To determine if fitness moderates the vascular response to acute inflammation with aging. We hypothesize that during acute inflammation A) high fit older adults will have similar endothelial and microvascular reactivity as young adults; B) high fit older adults will have greater endothelial and microvascular reactivity than low fit older adults.

Aim 2: To determine if antioxidant administration eliminates vascular dysfunction during acute inflammation. We hypothesize A) at baseline, ascorbic acid will improve endothelial function only in low fit older adults; B) during acute inflammation, ascorbic acid will improve vascular function to baseline values in young and older high fit adults.

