6.0 Study Design and Procedures

Study site

All study procedures except the vaccination will be conducted in the Integrative Physiology Laboratory at the University of Illinois at Chicago located at [name] in the Disability, Health and Social Policy building (DHSP). The typhoid vaccination will be administered by a registered nurse at the Clinical Research Center at UIC.

Design

A comparative, observational study design will be conducted with a group of 15 low fit young adults, 15 low fit older adults, and 15 high fit older adults, for a total of 45 research participants.

Subjects will participate in three study visits, with at least 72 hours between the first two visits, and exactly 24 hours between the last two visits. Menstruating females will be studied during the first 7 days of menses, or during the placebo phase if taking oral contraceptives. Participants will arrive to each visit having refrained from exercise, alcohol, and caffeine for 24h prior to each test day. Participants will be tested in the post-prandial (no food, only water) state (>10 hours) for all visits. (Figure 1)

[figure not shown]

Figure 1. Study protocol schematic

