Visit 1. Following informed consent, participants will complete a health history, food recall, and physical activity questionnaire and undergo anthropometric (height, weight, waist and hip circumference) and body composition measures (DEXA scan). For women of childbearing age, the first visit will include a urine pregnancy test using a test stick. Baseline influence of oxidative stress on endothelial and microvascular function will be assessed following supine rest and resting hemodynamics. Measures will include: 1) endothelial function, 2) microvascular function, 3) arterial stiffness, and 4) circulating markers of oxidative stress. Participants will then orally ingest 2g of ascorbic acid. This dose produces a physiological level of ascorbate in plasma[35], has been used in previous studies to improve endothelial function[35–39], and reaches optimal absorption after 2 hours[40,41]. During this time, an assessment of general cognitive function will be completed using the Montreal Cognitive Assessment (MOCA) and Symbol Digits Modality Test (SDMT), and be familiarized with a working memory cognitive function task (NBACK) by completing the task four times throughout the two hour period. Following 2 hours, all measures will be repeated to determine the influence of the antioxidant. The visit will finish with a treadmill exercise test to evaluate cardiorespiratory fitness (VO₂peak).

Visit 2. At least 72 hours later, participants will arrive after an overnight fast (>8 h) and undergo supine baseline measures of: 1) endothelial function, 2) microvascular function, 3) arterial stiffness, 4) cerebrovascular function and 5) cognitive function, 6) heart function and 7) circulating markers of inflammation

and oxidative stress. The typhoid vaccination (Typhuim Vi, Sanofi Pasteur SA) will then be administered by a registered nurse. Acute inflammation is often induced in cardiovascular research by use of either the influenza or typhoid vaccination [10,11,13,23,33,34,42]. Vaccinations provide a safe and controlled inflammatory response, in which the typhoid vaccination has shown to increase hsCRP up to at least 32 hours post-vaccination[13].

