Visit 3. Exactly 24-hours following Visit 2, participants will return to the lab under the same conditions. Visit 2 will be repeated. Following baseline measures, participants will consume 2g of ascorbic acid, as completed in Visit 1. Following 2 hours, measures of 1) endothelial function, 2) microvascular function, 3) arterial stiffness and 4) circulating markers of oxidative stress.will be repeated to determine the influence of the antioxidant.

All procedures are being completed for research purposes. The table below shows the estimated time commitment for each study visit and procedure.

	Visit 1	Visit 2	Visit 3
Informed Consent/ Questionnaires	30		
Anthropometrics	5		
DEXA	10		
Blood Draw	10	10	10
Rest/Preparation	10	10	10
Vascular Assessment			
Blood pressure	7	7	7
FMD/NIRS	13	13	13
Arterial stiffness (PWV)	10	10	10
Brain blood flow (TCD)		15	15
Carotid Flow		5	5
Heart Function		15	15
Cognitive: NBACK		12	
Vaccination		15	
Vit C	120		120
			Cognitive:
			NBACK
			MOCA
			SDMT
Blood Draw	10		10
Vascular Assessment			
Blood pressure	7		7
FMD/NIRS	13		13

Arterial stiffness (PWV)	10	10
Maximal Exercise Test	30	
TOTAL TIME (minutes)	285	112
Hours:	4.75	1.87
		245
		4.08

Measurements

DEXA Scan

We will determine percent body fat via a whole body scan by dual energy x-ray absorptiometry (GE, IDXA, Madison, Wi), which will be operated and calibrated using the manufacturer's stated guidelines. The duration of the scan will be less than 10 min and the subject will be exposed to a radiation dose of ≤ 0.3 mrem based upon the manufacturer's specifications and calculations from Standford Dosimetry, LLC RADAR Medical Procedure Radiation Dose Calculator. This amount of research protocol radiation exposure is minimal given the estimated effective equivalent dose is below the 100 mrem per year, a limit set by the Nuclear Regulatory Commission for "general public" exposure.

Venous blood samples

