9.0 Data Analysis

Statistical data analysis will be conducted using IBM SPSS statistical analysis software. This study is a hypothesis generating study, designed to test the anticipated relationship of fitness with aging on vascular function and oxidative stress during an acute bout of inflammation, in generally healthy individuals. This study will provide preliminary data to conduct power analyses for future studies.

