12.0 Statistical Considerations

The data will initially be examined for normality violations, entry errors, and missing values. Entry errors will be corrected by double-checking with original data files. Non-normally distributed data will have an appropriate transformation applied to achieve normality (i.e. log transformation, square root, etc.).

All analyses will be adjusted for age, sex, and body mass index, which are all factors known to influence hemodynamic parameters. Additionally, due to multiple tests, a correction will be applied for multiple comparisons (α divided by the number of tests). Significance level will be set at $\alpha=0.05$, with a Bonferroni correction used to correct for multiple comparisons.

Aim 1: The effects of acute inflammation on endothelial and microvascular function will be tested with a two-way group (3) by time (2) repeated measures ANOVA (V2 and V3 baseline). We expect older high fit adults to have similar vascular reactivity as young adults, i.e. decreased FMD and NIRS reperfusion, suggesting that fitness maintains vascular reactivity during an inflammatory insult with age. If no difference in the response to acute inflammation is seen between low and high fit older adults (not expected), this would indicate fitness is not protective with age during acute inflammation.

Aim 2: The effects of ascorbic acid ingestion will be tested with a two-way group (3) by time (2) repeated measures ANOVA to determine if the antioxidant caused changes at Visit 1 (baseline) or Visit 3 (acute inflammation). A two-way group (3) and time (3) repeated measures (V2 baseline, V3 before and after Vit C) ANOVA will determine if the antioxidant attenuated endothelial function during acute inflammation. At baseline, we expect ascorbic acid to improve vascular function, i.e. increase FMD and NIRS reperfusion, in older low fit adults, with no changes seen in young or high fit older adults. During acute inflammation, we expect ascorbic acid to restore vascular function to baseline in young and older high fit adults. If ascorbic acid does not alter vascular function during acute inflammation, this would indicate another mechanism other than oxidative stress is contributing to vascular dysfunction.

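### Minor: Aim 1 gives the Visit 1 resting FMD and NIRS readings no role, although Visit 1 rest to Visit 2 is the study's only vaccine-free resting repeat

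*Combined protocol and SAP*

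**What the plan says.** Section 12.0 (Statistical Considerations) tests Aim 1 with an analysis that "will be tested with a two-way group (3) by time (2) repeated measures ANOVA (V2 and V3 baseline"). In the young and high fit older groups it expects vascular reactivity to fall, "i.e. decreased FMD and NIRS reperfusion".

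Section 6.0 (Study Design and Procedures) takes the same measures at rest at Visit 1, before ascorbic acid: "Measures will include: 1) endothelial function, 2) microvascular function, 3) arterial stiffness, and 4) circulating markers of oxidative stress. Participants will then orally ingest" the antioxidant. They are repeated two hours later, and "The visit will finish with a treadmill exercise test to evaluate cardiorespiratory fitness". The visits are spaced "with at least 72 hours between the first two visits, and exactly 24 hours between the last two visits". The vaccine is given at Visit 2 after that visit's resting measures, and for Visit 3 "participants will return to the lab under the same conditions".

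All three groups of 15 are vaccinated; they differ by age and fitness only. Section 12.0 uses the Visit 1 vascular readings only in Aim 2, for the before-and-after test of ascorbic acid at that visit. The three-time Aim 2 model also starts at Visit 2.

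Section 12.0 says missing values will be examined but gives no rule for them. It divides alpha by the number of tests without giving that number. Section 9.0 calls the study hypothesis generating and adds: "This study will provide preliminary data to conduct power analyses for future studies".

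**The concern.** With no unvaccinated group, a change from Visit 2 to Visit 3 within a group mixes the vaccine response with ordinary visit-to-visit movement. The comparison between groups is protected from movement common to all groups, but a statement that one group fell is not. The plan makes such statements for the young and high fit groups, and Aim 2 then asks whether ascorbic acid brings those groups back to baseline.

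An illustration with assumed drift, since the documents give none: suppose there is no vaccine effect and resting readings drift by 0.3 or 0.5 SD of change. A paired test in one group of 15 (two-sided 0.05, before any multiplicity correction) is then significant with probability 19% or 44%.

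The plan collects one pair of readings that bears on this and leaves it unused. The same pair would give a vaccine-free within-person SD. The pilot data in Section 2.0 do not: they cover NIRS in young adults only, across a vaccine interval, with no within-person correlation.

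**Working it through.** The plan states no power, effect size or variance for this analysis, so there is no figure of its own to reproduce. The correlations and missing rates below are assumptions.

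**1. Which pairs are free of vaccine and ascorbic acid?** FMD and NIRS are read five times: V1 rest, V1 post-ascorbic acid, V2 rest (before vaccine), V3 rest, V3 post-ascorbic acid.
- V1 rest to V1 post, and V3 rest to V3 post: same-day ascorbic acid.
- V1 post to V2: starts from a same-day ascorbic acid reading.
- Any pair from V1 or V2 to V3: spans the vaccine.
- V1 rest to V2: neither. It is the only such pair.

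**2. How tightly would V1 rest to V2 change be estimated?** Take variance 1 per reading and V1-V2 correlation r from 0.8 to 0.5. The 95% half-width is t × √[2(1−r)/n], in SDs of a single reading.
- All 45: 2.015 × √(0.4/45) = 0.19; 2.015 × √(1.0/45) = 0.30.
- One group of 15: 2.145 × √(0.4/15) = 0.35; 2.145 × √(1.0/15) = 0.55.
- Two groups compared: t on 28 df × √[2(1−r) × 2/15] = 0.47 to 0.75.

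In SDs of change the half-widths do not depend on r: 2.015/√45 = 0.30 overall and 2.145/√15 = 0.55 in one group. If V1-V2 and V2-V3 changes have similar SDs, one group's interval cannot exclude even the 0.5 SD drift used above. The within-person SD on 42 df has 95% limits √(42/χ²) = 0.82 to 1.27 times the estimate, that is −18% to +27%.

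**3. Does V1 sharpen the V3−V2 contrast?** Seven correlation sets r12/r13/r23 were tried: 0.6/0.6/0.6, 0.6/0.6/0.7, 0.6/0.5/0.7, 0.5/0.5/0.8, 0.8/0.64/0.8, 0.7/0.49/0.7, 0.729/0.656/0.9. The generalised least squares variance from all available readings was divided by the complete-case variance 2(1−r23)/(1−q)², with a fraction q of readings missing independently.

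| q | Complete cases of 45 | V2 and V3 only, all available | Adding V1 |
|---|---|---|---|
| 0 | 45 | 1.000 | 1.000 |
| 0.05 | 45 × 0.9025 = 40.6 | 0.979-0.995 | 0.969-0.987 |
| 0.10 | 45 × 0.81 = 36.5 | 0.957-0.989 | 0.937-0.974 |

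The cut is 1.3%-3.1% at 5% missing and 2.6%-6.3% at 10%. Of that, V1 itself supplies 0.3-3.1 percentage points; the rest comes from not dropping people. With the covariance estimated from 45 people (simulation, five of the sets), the cuts are 0.3%-3.4% and 2.7%-6.2%.

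**4. Holm against Bonferroni.** Assume three pairwise tests, 15 per group, 42 df, young equal to high fit, and low fit different by 0.8 SD of change (200,000 simulations).

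| | Each true contrast | Both true contrasts |
|---|---|---|
| Bonferroni | 39% | 24% |
| Holm | 42% | 29% |

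The exact noncentral-t value for Bonferroni per contrast is 39.1%. These effects are in SDs of change and the half-widths in step 2 mainly in SDs of a reading, so they must not be compared directly: 0.8 SD of change is 0.8 × √[2(1−r23)] SD of a reading, which is 0.72 at r23 = 0.6 and 0.36 at r23 = 0.9. Age, sex and BMI are taken as person-level main effects, which drop out of within-person change.

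**The case against.** The case for leaving the plan alone is strong on several counts.

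- **The main test is sound.** Aim 1's hypotheses are between groups, and group-by-time cancels drift common to all groups. V2 is a defensible baseline, 24 hours before V3 and under matched conditions. This stands. A reader might infer that the missing unvaccinated group or the unused V1 reading invalidates Aim 1; the documents do not support that.
- **The low fit older group is a concurrent check.** It is expected not to fall, so common drift would show there over the same 24 hours. This stands in part: that group is vaccinated, so its change is not vaccine-free.
- **V1 to V2 is a poor control.** The gap has no upper limit. Ascorbic acid and a treadmill test come between, and Aim 2 expects a group-specific response ("at baseline, ascorbic acid will improve endothelial function only in low fit older adults"), although carry-over beyond 72 hours is not shown. Section 6.0 requires more than 10 hours without food at all visits but more than 8 for Visit 2; those passages need reconciling. Menstruating women may be tested in different cycles, chiefly in the young group. All of this stands, so the change is a reference and not a correction.
- **A future study of the vaccine response needs the SD of V3−V2, which the plan already supplies.** This largely stands. The vaccine-free SD is an addition.
- **The precision gain rests on assumed missingness.** This stands. If loss is by dropout (V1 always present, 10% lost at each later visit), V1 itself adds only 0.2-1.1 points over the same seven sets.
- **Bonferroni is valid.** It is; Holm controls the same familywise error with at least as much power.

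Three stronger uses of the data are tempting and should be resisted.

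- **Pooling V1 with V2 as a common baseline.** Under equal correlations and equal weights this cuts the variance of change by 25% (from 2 to 1.5 within-person variances). Over the seven sets, with the weight estimated, the ratio is 0.77-1.02. Pooling also does worse than V2 alone once two groups differ in V1-V2 change by about one standard error, √[2(1−r) × 2/15] = 0.23-0.37 SD of a reading. That is half of what the 95% interval could detect.
- **Subtracting the V1-V2 change.** Under equal correlations this triples the variance (from 2 to 6 within-person variances).
- **Testing the three pairs at 0.05 only after a significant group-by-time F test.** This controls error within one outcome only. With a simulated 4.9% per outcome, two independent outcomes give 1 − 0.951² = 9.6%, whereas the plan corrects over its number of tests.

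**Conclusion.** The point holds as a minor, cheap improvement. From the text alone, Aim 1 uses V2 and V3 only, resting FMD and NIRS exist at Visit 1, no group is unvaccinated, and nothing compares V1 rest with V2. The loss is in interpretation: the plan expects a within-group fall but has no vaccine-free yardstick for it, and one vaccine-free repeatability estimate goes unreported.

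The loss is not one of validity and hardly one of power. With complete data the gain for V3−V2 is nil. With 5%-10% of readings missing it is about 1%-6% of variance, partly from the model rather than V1. The yardstick can exclude only fairly large drift, especially in a single group. Holm adds about 3 points of power per contrast and 5 for both, under an assumed three-test family and an assumed 0.8 SD of change. All sizes depend on correlations, missing rates and effects that the documents do not give.

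**What to change.** 1. **Report V1 rest to V2 change**, overall and by group, with 95% CI and within-person SD, for outcomes measured at Visit 1. Limit this to eligible, group-assigned participants: fitness is measured only at the end of Visit 1, and Section 4.2 excludes the 51st-74th percentile, so some Visit 1 readings will belong to no group. Label it an imperfect reference and list the limits above. Do not subtract it or use it to justify pooling.
2. **Keep V3 rest minus V2 by group as the main contrast**, but fit a linear mixed model to all available V1 rest, V2 and V3 rest readings of those participants. Use group, occasion, their interaction, age, sex and BMI, with unstructured covariance and small-sample degrees of freedom. People with one missing reading then stay in.
3. **State the number of tests and use Holm** in place of Bonferroni across that number. In any power statement, say that the 0.8 SD is an SD of change.

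The cost is plan wording and slightly more analysis, with no new visit, measurement or participant burden. The one downside of Holm is that simultaneous confidence intervals are less simple than under Bonferroni.

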To understand the vascular response to acute inflammation, an integrative approach must be applied to identify both the mechanism of vascular dysfunction and a potential therapeutic target to abrogate acute inflammation-induced vascular dysfunction. This study addresses both gaps of knowledge by investigating the role of oxidative stress and by recruiting participants based on training levels to effectively examine the effect of high fitness.

Relevance

[figure not shown]
CV disease is the leading cause of death in the United States and particularly burdens older individuals[31]. Aerobic exercise is recommended by the United States Physical Activity Guidelines, American Heart Association, and American College of Sports Medicine (ACSM) to improve quality of life, reduce risk of heart disease, diabetes, stroke, and osteoporosis, and improve immune function. If fitness moderates the effects of acute inflammation on vascular function, our study will provide insight into how physical activity and exercise interventions could reduce the risk of CV events during acute inflammation.

Preliminary Studies

Our laboratory has conducted a series of studies evaluating the effect of acute inflammation on cardiovascular function[15–17,32–34]. evaluated both cardiac and endothelial function during acute inflammation in younger and older adults[16,17,34]. These studies suggest age-associated differences in endothelial function, cardiac function, and blood pressure that may be detrimental to older adults[16,33,34]. We have shown that fitness, an indicator of chronic exercise, may exert protective effects. In older adults, high fitness protected from acute inflammation-induced arterial stiffening[15].

Recently our lab has shown that high fit older adults also have a similar endothelial response to acute inflammation as younger adults. The high fit older adults exhibit a greater reduction in flow-mediated dilation than older low fit adults. Fitness level did not influence the response in young adults (Figure 2)[23]. Additionally, we have collected pilot data on microvascular reactivity in young adults ($n=16$), showing no changes in tissue saturation index from baseline to 24h during acute inflammation in peak hyperemic response ($13.7\pm3.9\%$ to $13.8\pm2.9\%$) or reperfusion slope ($1.84\pm0.52\%/\text{s}$ to $1.83\pm0.49\%/\text{s}$).

Figure 2

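### Aim 2B conclusions on NIRS do not require a fall after vaccination, although the plan's own pilot in young adults showed none

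*Combined protocol and SAP*

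**What the plan says.** **Expected response to vaccination.** For Aim 1, Section 12.0 expects older high fit adults to react as young adults do, "i.e. decreased FMD and NIRS reperfusion". Young adults are the reference pattern, so a fall in NIRS reperfusion is expected in them.

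**Pilot.** Section 2.0 (Preliminary Studies) describes NIRS data from 16 young adults as "showing no changes in tissue saturation index from baseline to 24h during acute inflammation". Peak hyperemic response went from 13.7 ± 3.9% to 13.8 ± 2.9%, and reperfusion slope from 1.84 ± 0.52 to 1.83 ± 0.49 %/s.

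**Restoration.** Hypothesis 2B in Section 3.0 is that "during acute inflammation, ascorbic acid will improve vascular function to baseline values in young and older high fit adults". Section 12.0 repeats it: "During acute inflammation, we expect ascorbic acid to restore vascular function to baseline in young and older high fit adults". In its expectation for vitamin C at baseline, Section 12.0 explains vascular function as FMD together with NIRS reperfusion. No criterion or margin for restoration is given, and no prior fall is required.

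**Tests and null rule.** Section 12.0 plans a group-by-time ANOVA before and after vitamin C at Visit 1 or Visit 3, and a three-time-point ANOVA (Visit 2 baseline, Visit 3 before and after vitamin C). It adds that if vitamin C leaves vascular function unchanged during inflammation, something other than oxidative stress is contributing to the dysfunction.

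**The concern.** The expected NIRS fall in young adults is the premise of Aim 2B on that outcome, and the only NIRS data in the plan do not show it. The plan does not reconcile the two statements or say what follows if the fall is absent.

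Two unsupported conclusions then become possible. The null rule takes vascular dysfunction as given: with no fall and no vitamin C effect, it would point to another mechanism for a dysfunction that did not occur. Alternatively, if restoration were judged by the final level alone, an unchanged NIRS value would be credited to the antioxidant. The first blames another mechanism and the second supports oxidative stress, from the same data. The sound conclusion, that Aim 2B is untestable on NIRS in that group, is not provided for. Section 9.0 says the results are meant to inform later studies, so a mechanism claim made this way would carry forward.

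**Working it through.** **Inputs**
- Pilot means and spreads as quoted above, n = 16 (Section 2.0); ± is read as SD.
- 15 participants per group (Section 6.0, Design).
- Alpha 0.05 with Bonferroni correction (Section 12.0). The number of tests is not given, so 0.05 and 0.05/3 are shown. Tests are assumed two-sided.
- Within-person correlation r between measurements is not given; assumed 0.5 to 0.9.

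**Step 1. Check the pilot's no-change statement.** The plan states no power or sample-size figure, so this is the figure to reproduce.

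Change in slope = 1.83 - 1.84 = -0.01 %/s, or -0.5% of baseline.

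SD of change = sqrt(0.52² + 0.49² - 2r × 0.52 × 0.49); SE = SD/√16; interval = -0.01 ± 2.13 × SE (t on 15 df).

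At r = 0.5: sqrt(0.2704 + 0.2401 - 0.2548) = 0.506; SE = 0.126; half-width = 0.27.

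| r | SD of change | 95% interval, %/s | % of baseline | p |
|---|---|---|---|---|
| 0.5 | 0.506 | -0.28 to 0.26 | -15 to +14 | 0.94 |
| 0.7 | 0.392 | -0.22 to 0.20 | -12 to +11 | 0.92 |
| 0.9 | 0.228 | -0.13 to 0.11 | -7 to +6 | 0.86 |

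For the peak response, the change is +0.1 percentage points (+0.7%), with p from 0.91 (r = 0.5) to 0.83 (r = 0.9). The pilot's statement agrees with its own figures, but the slope data leave room for a fall of roughly 7% to 15%.

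**Step 2. Follow the plan's logic when there is no NIRS fall and vitamin C is inert.**
- The before/after test at Visit 3 is usually null. The null rule then says another mechanism contributes to vascular dysfunction, although none was shown on NIRS.
- If restoration means only that the Visit 3 value after vitamin C does not differ significantly from Visit 2, it is met by default.
- If restoration also needs a rise at Visit 3 from before to after vitamin C, it is rarely met.

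**Step 3. Put sizes on the readings.** Simulation of one group of 15 at three time points: SD 0.5 %/s, r = 0.5, 0.7 and 0.9, true fall 0.01 %/s as in the pilot, vitamin C effect zero, paired t-tests without covariates, 40,000 trials per setting.

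| Event | Alpha 0.05 | Alpha 0.05/3 |
|---|---|---|
| Post-vitamin C value not significantly different from Visit 2 | about 95% | about 98% |
| Significant rise at Visit 3, before to after | about 2.5% | about 0.8% |
| Significant fall, significant rise, and no difference from Visit 2 | about 0.5% | about 0.1% |

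The first row is close to 1 minus alpha, as for any comparison with no true difference. It measures what the level-only reading would allow; it is not a property of this trial's data.

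The level-only reading is also weak when a real fall exists. With a true 10% fall (0.184 %/s) and inert vitamin C, the post-vitamin C value is non-significant against Visit 2 in 73%, 60% and 16% of trials at r = 0.5, 0.7 and 0.9 (alpha 0.05).

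**The case against.** A reader might infer that restoration on NIRS would be declared, and reported as antioxidant rescue, even if vitamin C did nothing. The documents do not support that. Hypothesis 2B says improve, which an inert agent does not do. Section 12.0 plans a direct before/after test at Visit 3, and its null rule counts an inert vitamin C against oxidative stress. Nowhere does it say that a non-significant difference from Visit 2 counts as restored. The 95% figure therefore applies only to a reading that the plan leaves open.

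A reader might also infer from the pilot that there is nothing to restore. That goes too far: 16 young adults of unstated fitness cannot exclude a modest fall, the pilot description does not name the inflammatory stimulus, and there are no pilot NIRS data in older high fit adults. The sentence on the three-time-point ANOVA names endothelial function only; its extension to NIRS is an inference from the broader term vascular function. The study is also described as hypothesis generating.

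These points limit the claim but do not remove it. The Visit 3 test protects against a false restoration claim only if a rise is required, and the plan does not say so. The null rule cannot be applied soundly where no dysfunction has been shown. Neither gap is closed by the exploratory purpose.

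**Conclusion.** The point holds in a limited form. Section 12.0 expects a NIRS fall in young adults that the plan's pilot did not show (-0.01 %/s; interval -0.28 to 0.26 at r = 0.5, -0.13 to 0.11 at r = 0.9), and Aim 2B conclusions do not depend on that fall being demonstrated. Without it, the stated null rule yields an unsupported mechanism conclusion. A level-only reading, if adopted, would be met by an inert antioxidant in about 95% of trials at alpha 0.05, against about 2.5% or less once the Visit 3 rise is also required.

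These sizes rest on assumed correlations, ± read as SD, two-sided paired tests and 15 per group. The pilot evidence concerns NIRS in young adults only. It does not bear on FMD, for which Section 2.0 reports a fall in younger adults, or on older high fit adults. The Aim 1 test itself is unaffected if two-sided.

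**What to change.** In Section 12.0:
1. Reconcile the NIRS expectation for young adults with the pilot: either state that no change is expected, or say why a fall is still expected.
2. For each outcome and group, claim restoration only if there is a demonstrated fall from Visit 2 to Visit 3 before vitamin C, and a demonstrated rise from before to after vitamin C at Visit 3.
3. Apply the rule about another mechanism only where that fall is shown.
4. Otherwise report the vitamin C effect with its confidence interval, and draw no restoration or mechanism conclusion for that outcome and group.

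The change is to wording only; no participants, visits or measurements are added. The cost is that fewer Aim 2B claims will be possible with 15 per group. For reperfusion slope, using the pilot SDs and a paired test in one group, power to show a 10% fall is 0.26 at r = 0.5 and 0.83 at r = 0.9 (alpha 0.05), or 0.13 and 0.66 at alpha 0.05/3. For a 20% fall it is 0.75 and 1.00, or 0.55 and 1.00. A group in which a modest fall is missed would give an estimate and an interval but no claim, which suits a study meant to generate hypotheses.
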